### 6.2.3. Handling of Missing Data

Missing data will not be imputed unless otherwise specified. Missing dates or partially missing dates will be imputed conservatively for adverse events and prior/concomitant medications/procedures. Specific rules for the handling of missing or partially missing dates for adverse events and prior/concomitant medications/procedures are provided in [Appendix A](#).

By-visit endpoints will be analyzed using observed data unless otherwise specified. For observed data analyses, missing data will not be imputed, and only the observed records will be included.

### 6.2.4. Multiplicity Adjustment

No multiplicity adjustments will be made in this study.

### **6.2.5. Data Integrity**

Before pre-specified final analysis begins, the integrity of the data should be reviewed to assure fit-for-purpose. The data set for analysis should be an accurate and complete representation of the subjects' relevant outcomes from the clinical database. All data should be complete and reviewed up to a pre-specified cutoff date. Consistency checks and appropriate source data verification should be completed.

## **6.3. Subject Characteristics**

### **6.3.1. Subject Disposition**

The number (percentage) of subjects randomized, treated, discontinued from the study drug and/or study will be counted by treatment group. The primary reason for subjects randomized but not treated and study drug and/or study discontinuation will be summarized according to the categories in the eCRF. A listing of subject disposition will be provided.

### **6.3.2. Protocol Deviations**

Important protocol deviation criteria will be established, and subjects with important protocol deviations will be identified and documented before the database lock.

Important protocol deviations will be summarized and listed by category for all subjects in the Safety Analysis Set. Deviation categories are not mutually exclusive. Multiple deviations within the same category are counted once per subject.

### **6.3.3. Demographic and Other Baseline Characteristics**

Demographics and other baseline characteristics will be summarized by treatment group using descriptive statistics in the Safety Analysis Set. Summary statistics will be presented for continuous variables, and the number (percentage) of subjects in each category will be presented for categorical variables. Continuous variables include but are not limited to age, height, weight, and BMI. Categorical variables include but are not limited to sex, race, and ethnicity. A listing of demographics and other baseline characteristics will be provided.

### **6.3.4. Prior and Concomitant Medications**

Prior medications will be defined as medications that started and stopped before the dose of study drug. Concomitant medications will be defined as medications that (1) started before the dose of study drug and were continuing at the time of the dose of study drug, or (2) started on or after the date of the dose of study drug up to 30 days after the dose of study drug.

Prior and concomitant medications will be coded using the version of World Health Organization Drug Dictionary (WHO DD) drug codes currently in effect at BeiGene at the time of database lock. They will be further coded to the appropriate Anatomical Therapeutic Chemical (ATC) code indicating therapeutic classification.

The number (percentage) of subjects reporting prior and concomitant medications will be summarized by ATC medication class and WHO DD preferred name in the Safety Analysis Set. A listing of prior and concomitant medications will be provided.

### 6.3.5. Medical History

Medical History will be coded using Medical Dictionary for Regulatory Activities (MedDRA) version currently in effect at BeiGene at the time of database lock. The number (percentage) of subjects reporting a history of any medical condition, as recorded on the CRF, will be summarized by system organ class (SOC) and preferred term (PT) in the Safety Analysis Set. A listing of medical history will be provided.

## 6.4. Efficacy Analysis

There is no efficacy analysis planned for this study.

## 6.5. Safety Analyses

All safety analyses will be performed based on the Safety Analysis Set. Descriptive statistics will be used to analyze all safety data.

### 6.5.1. Extent of Exposure

The extent of each study drug exposure will be summarized descriptively for the study drug(s) administered by treatment group. The number (percentage) of subjects with dose interruption and infusion rate decreased will be summarized with the respective reasons by treatment group for each drug.

Subject data listings will be provided for all dosing records.

### 6.5.2. Adverse Events

The AE verbatim descriptions (investigator terms from the eCRF) will be classified into standardized medical terminology using MedDRA. Adverse events will be coded to the MedDRA lowest level term closest to the verbatim term, along with the linked MedDRA PT and primary SOC.

A TEAE is defined as an AE that had an onset date or a worsening in severity from baseline on or after the administration of study drug and up to 30 days after the dose of study drug. Summary tables will generally focus on those AEs that were treatment-emergent. All AEs, treatment-emergent or otherwise, will be presented in subject data listings.

If any of the following TEAEs occurs, the administration of the study drug and the enrollment of new subjects will pause for the current cohort:

- One or more  $\geq$  Grade 4 TEAEs or treatment-emergent SAEs related to study drug(s) as assessed by the investigator in any subject or
- One or more Grade 3 TEAEs related to study drug(s) as assessed by the investigator in 2 or more subjects at the same cohort.

An AE overview table, including the number of subjects with TEAEs, TEAEs with grade 3, TEAEs with grade 4 or higher, treatment-emergent serious adverse events (SAEs), TEAEs that led to death, TEAEs that led to treatment discontinuation, TEAEs that led to treatment modification for study drug, and treatment-related TEAEs, will be provided by treatment group. Treatment-related AEs include those events considered by the investigator to be related to study drug or with a missing assessment of the causal relationship.

The incidence of TEAEs will be reported as the number (percentage) of subjects with TEAEs by SOC, PT and the worst grade. A subject will be counted only once by the highest severity grade according to [NCI-CTCAE version 5.0](#) within a SOC and PT, even if the subject experienced more than one TEAE within a specific SOC and PT. The number (percentage) of subjects with TEAEs will be summarized by SOC and PT.

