The planned cohorts and number of subjects in each cohort are provided in [Table 3](#). Up to 30 subjects (including possible replacement) will be enrolled in the study, which will be conducted in 1 to 2 centers in Australia.

Subjects are expected to be available for follow-up visits until Day 113 of the study. Subjects will be replaced if they cannot complete the infusion or they do not receive any study drug after randomization. Subjects may be replaced if they discontinue from the study before Day 29.

Table 3: Planned Cohorts and Number of Subjects in Each Cohort

Part	Cohort	Number of Subjects in Each Cohort	
		Active Arm	Control Arm (Normal Saline)
1: BGB-DXP604 alone	1A: 10 mg/kg	6	2
	1B: 30 mg/kg ^a	6	2
2: BGB-DXP604 + BGB-DXP593	2A: 30 mg/kg ^b BGB-DXP604 + 30 mg/kg ^b BGB-DXP593	6	2

Abbreviation: SMC, Safety Monitoring Committee.

^a The dose level of BGB-DXP604 in Cohort 1B may be adjusted based on SMC recommendation.

^b The doses of BGB-DXP604 and BGB-DXP593 in Cohort 2A will be recommended by SMC and not exceed 30 mg/kg for each study drug.

Study Assessments

Subjects will be monitored throughout the study for safety, tolerability, PK, and immunogenicity of BGB-DXP604 and BGB-DXP593.

Assessments of safety will include adverse events (AEs), SAEs, clinical laboratory tests, physical examinations, vital signs, and ECGs. An SMC will periodically monitor safety data.

AEs will be graded for severity per the current version of the National Cancer Institute-Common Terminology Criteria for Adverse Events version 5.0 (NCI-CTCAE v5.0). Refer to Section 9 for additional and specific information regarding AE monitoring and reporting.

PK and ADA sampling will be collected at specific intervals from Day 1 to Day 113 ([Appendix 2](#) and [Appendix 3](#)).

Study procedures and assessments are further detailed in Section 7 and Section 8, respectively, and the Schedule of Assessments can be found in [Appendix 1](#). Specific details regarding dose escalation are described in the following sections.

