9.7. Timing, Frequency, and Method of Capturing Adverse Events and Serious Adverse Events

9.7.1. Adverse Event Reporting Period

After informed consent has been signed but before administration of the study drug(s), only SAEs should be reported.

After initiation of the study drug(s), all AEs and SAEs, regardless of relationship to study drug(s), will be reported until 30 days after the administration of study drug(s) or the EOS Visit, whichever is later. After the period, the investigator should report any SAEs that are considered to be related to the study drug(s).

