10.3.2. Adverse Events

The AE verbatim descriptions (as recorded by the investigator on the eCRF) will be classified into standardized medical terminology using the Medical Dictionary for Regulatory Activities (MedDRA). AEs will be coded to MedDRA by the lowest level term, preferred term (PT), and primary system organ class (SOC).

A TEAE is defined as an AE that had an onset date or a worsening in severity from baseline on or after the administration of study drug(s) and ≤ 30 days after the administration of study drug(s). Only those AEs that were treatment emergent will be included in summary tables.

The incidence of TEAEs will be reported as the number (percentage) of subjects with TEAEs by SOC and PT. A subject will be counted only once by the highest severity grade according to NCI-CTCAE v5.0 within a SOC and PT, even if the subject experienced ≥ 1 TEAE within a specific SOC and PT. The number (percentage) of subjects with TEAEs will also be summarized by relationship to the study drug(s).

Treatment-related AEs include those events considered by the investigator to be related to study drug(s) or with missing assessment of the causal relationship. Treatment-emergent SAEs and treatment-related TEAEs will be summarized. All AEs, treatment-emergent or otherwise, will be presented in subject data listings.

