### 4. STUDY ENDPOINTS

#### 4.1. Primary Endpoint(s)

- Incidence and severity of treatment-emergent adverse events (TEAEs) and treatment-emergent serious adverse events (SAEs)

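### AEs starting more than 30 days after dosing are collected to Day 113 but enter no planned AE table; a second set of tables through end of study would close the gap

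*SAP*

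**What the plan says.** The primary endpoint is the incidence and severity of TEAEs and treatment-emergent SAEs (Protocol 2.2.1, SAP 4.1). SAP 6.5.2 defines a TEAE as an AE with onset, or worsening from baseline, "on or after the administration of study drug and up to 30 days after the dose of study drug". Protocol 10.3.2 gives the same 30 days.

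Collection runs longer. Under Protocol 9.7.1, all AEs and SAEs, related or not, "will be reported until 30 days after the administration of study drug(s) or the EOS Visit, whichever is later". For a subject who completes the visits, the EOS Visit is Day 113 (Protocol 7.6.2), and Protocol 3.1 says: "Subjects are expected to be available for follow-up visits until Day 113 of the study".

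On tabulation, Protocol 10.3.2 is strict: "Only those AEs that were treatment emergent will be included in summary tables". SAP 6.5.2 is looser: "Summary tables will generally focus on those AEs that were treatment-emergent". Even so, each AE table that the SAP names (the overview, SOC/PT by worst grade, and SOC/PT) is a table of TEAEs. Later events go to listings: "All AEs, treatment-emergent or otherwise, will be presented in subject data listings".

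Neither document gives a reason for 30 days or states a projected human half-life.

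**The concern.** The main output of this first-in-human study is its AE tables. As planned, a treatment-related SAE that began on Day 40 would be collected and reported to the sponsor, yet the tables would show nothing for it. A reader who goes to the overview table for the safety result could miss it.

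The later period is not idle. The antibody is projected to clear slowly, ADA sampling continues to Day 113, and both documents leave room for an evaluation of immunogenicity against safety (Protocol 10.5, SAP 6.7). Laboratory, vital-sign and ECG summaries are by visit, and the laboratory shift table takes the maximum postbaseline grade, with no 30-day limit (SAP 6.5.3 to 6.5.5). A Grade 3 laboratory value in week 12 would thus enter the shift table, while a new AE recorded for it would enter no AE table.

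**Working it through.** **Calendar time.** Dosing is on Day 1, so Day 113 is 112 days after the dose. Time after the window closes: 112 − 30 = 82 days, and 82/112 = 73%.

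**Scheduled visits (Protocol Appendix 1).** Of the 13 post-dose visits for completers, 8 fall inside the window (D2, D3, D4, D5, D8, D15, D22, D29) and 5 after it (D43, D57, D71, D85, D113).

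**ADA samples (Protocol Appendix 3).** Post-dose samples are at D15, D29, D57, D85 and D113. The last three of the five fall after the window.

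**Projected exposure.** The inputs are the human projections for BGB-DXP604 in Protocol Table 1: CL 0.0090 L/h, Vc 3.79 L, Q 0.031 L/h, Vp 1.92 L.

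1. Reproduce Table 1. Protocol 1.4.2.1 scales monkey values by the body-weight ratio, to the power 0.75 for CL and Q and 1.0 for volumes. The ratio is not given; Vc implies 3.79/0.162 = 23.4. Then CL = 0.00085 × 23.4^0.75 = 0.00904 (table 0.0090), Q = 0.0029 × 23.4^0.75 = 0.0308 (table 0.031) and Vp = 0.0822 × 23.4 = 1.92 (table 1.92). All agree to rounding.
2. Rate constants per hour: k10 = CL/Vc = 0.002375; k12 = Q/Vc = 0.008179; k21 = Q/Vp = 0.016146. Their sum is s = 0.026700.
3. Terminal rate: β = [s − √(s² − 4·k10·k21)]/2 = 0.001523 per hour. Half-life = ln 2/β = 455 h = 18.97 days. Rounding of the table entries allows 18.8 to 19.1 days.
4. Range: multiplying CL by exp(±0.301), one SD of the monkey between-animal variability, gives 14.2 to 25.4 days. The documents give no human variability, so this range is an assumption.
5. Window in half-lives: 30/18.97 = 1.6 (30/25.4 = 1.2 to 30/14.2 = 2.1). To Day 113: 112/18.97 = 5.9.
6. Share of AUC after day 30, treating the infusion as a bolus. The fast rate is α = s − β = 0.025177. The coefficients are A = (α − k21)/(α − β) = 0.382 and B = (k21 − β)/(α − β) = 0.618. The share is (B/β)·exp(−720β)/(A/α + B/β) = 405.9 × 0.334/421.1 = 32%. The share after day 112 is 1.6%.
7. Serum level at day 30 relative to the initial level: 0.618 × 0.334 = 21%.

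**One subject.** With 6 active subjects per cohort, one subject is 1/6 = 16.7 percentage points in a table row. That is the size of the omission only if the subject has no qualifying event in that row within 30 days, because each subject is counted once.

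**The case against.** The case against is substantial, and much of it stands.

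- Protocol and SAP give the same window, so there is no contradiction. Protocol 7.6.3 schedules a 30-day safety visit for subjects who leave early, which makes 30 days a period that completers and early leavers can share. Collecting for longer than one tabulates is a legitimate choice.
- No data are lost. Late events are listed, and with at most 30 subjects the listing can be read in full. SAEs go to the sponsor within 24 hours, and the SMC can recommend suspension on suspected risk (Protocol 3.4).
- A reader might infer that most of the safety follow-up is discarded. That is true only in calendar days: 8 of 13 post-dose visits and about 68% of projected AUC lie inside the window, and the other safety summaries have no 30-day cut-off.
- A reader might infer that delayed or ADA-associated reactions cannot reach the primary endpoint. The definition excludes only onset or worsening after day 30. Earlier reactions count however long they last, and the D15 and D29 ADA samples fall in that period.
- Concomitant medications share the limit (SAP 6.3.4: "started on or after the date of the dose of study drug up to 30 days after the dose of study drug"). All medications taken during the study are recorded and a listing is planned, so no consequence for the safety conclusions is shown.

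What remains is narrow but real: an event with late onset, however serious or related, is in no AE table that the SAP names. The SAP's looser wording would permit such a table but does not plan one.

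**Conclusion.** The point holds as a recommended improvement. It is not a must-fix error. The planned AE tables cover 30 of 112 days, while the events of the other 82 days are already being collected.

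The exposure argument rests on a half-life of about 19 days that is derived from monkey scaling, not stated, and that applies to BGB-DXP604 only. The documents give no PK parameters for BGB-DXP593, so nothing comparable can be said for the second antibody in Cohort 2A. The calendar figure depends on none of this, but it assumes a subject who stays to Day 113.

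It is tempting to conclude that the tables understate risk by design, or that the TEAE definition itself should be moved to Day 113. The documents support neither step. Whether any late event would be drug-related is unknown, and Protocol 1.5 considers a pharmacodynamic effect in healthy subjects unlikely. The pausing criteria (Protocol 3.4, repeated in SAP 6.5.2) are worded in terms of TEAEs, so redefining the term would also change them.

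**What to change.** Keep the 30-day TEAE definition and its tables as the primary summary. Add to SAP 6.5.2 a second version of the overview table and of the SOC/PT by worst grade table, including SAEs and treatment-related AEs. These should cover all AEs from dosing through the EOS Visit, by treatment group. For a subject whose EOS Visit comes before day 30, run them to day 30, as Protocol 9.7.1 already does for collection. Show follow-up time or the number still followed in each group. Because Protocol 10.3.2 confines summary tables to TEAEs, record the addition in SAP Section 8, where one change from the protocol is already logged.

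The pausing criteria do not say which period they cover beyond their use of the term TEAE. The sponsor should reconcile Protocol 3.4 and SAP 6.5.2 with the TEAE definition so that the window is explicit. The added tables should leave those criteria unchanged.

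The cost is a SAP revision and one repeated set of tables, with no new data. The added tables will pick up some unrelated background events, which the placebo group helps to interpret. Follow-up will be unequal where subjects leave early, for example after a positive COVID-19 test or withdrawal of consent, so crude percentages need the follow-up figures beside them.

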1.5. Benefit-Risk Assessment

This is a FIH study for BGB-DXP604 and the side effects of BGB-DXP604 in humans are unknown.

The healthy subjects in this study will not receive any health benefit from participating in the study other than an assessment of their medical status.

The subjects might have some discomfort from blood collection and other study procedures. Other than that, the risks of study participation include possible adverse reactions associated with BGB-DXP604, such as infusion-related reactions. However, because BGB-DXP604 is a human protein selected from recovered COVID-19 patients, it is unlikely to have any pharmacodynamic effect in healthy subjects. Therefore, the risks are generally low under the current safety monitoring planned for this study.

As exogenous proteins, BGB-DXP604 used alone or in combination with BGB-DXP593 might lead to hypersensitivity reactions, although immunogenicity is considered low due to its human origin. Potential antibody dependent enhancement (ADE) has been observed in some viral infections, such as dengue fever. The possibility of ADE with passive immunity cannot be excluded in COVID-19. However, clinical experiences with respiratory syncytial virus, influenza, and dengue provide strong evidence that the circumstances thought to lead to ADE of disease—including low affinity or cross-reactive antibodies with limited or no neutralizing activity or suboptimal titres—are very rarely implicated as the cause of severe viral infection in the human host (Arvin et al 2020). BGB-DXP604 and BGB-DXP593 are highly potent neutralizing antibodies, and thus are unlikely to cause ADE. In addition, a large number of COVID-19 patients have received convalescent plasma therapy, where no hints of ADE have been identified (Joyner et al 2020).

To further minimize the risk to the subjects, the method of sentinel dosing will be adopted for this study and each healthy subject in the study will receive only a single dose of study drug(s).

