3.4. Criteria for Pausing Drug Administration and New Enrollment

In this study, the SMC will review the safety and laboratory data for each cohort. If an increased risk for the subjects is suspected during the study, the SMC will recommend to immediately suspend the recruiting of additional participants.

Administration of study drug(s) and enrollment of new subjects will be paused for the current cohort if any of the following events occurs:

- One or more \geq Grade 4 TEAEs or treatment-emergent SAEs related to study drug(s) as assessed by the investigator in any subject or
- One or more Grade 3 TEAEs related to study drug(s) as assessed by the investigator in ≥ 2 subjects in the same cohort.

The SMC may recommend keeping the current enrollment plan, opening a repeated cohort at the same dose of study drug(s), de-escalating to a lower dose of study drug(s), or terminating the study. For the repeated cohort at the same dose level and the cohort at the lower dose level, the number of subjects and randomization ratio will be the same as planned for each cohort.

If the TEAE(s) previously observed at the same dose level occurs again in a repeated cohort at the same dose level, no higher dose level will be tested in Part 1. If the same situation occurs in the repeated cohort in Part 2, no combination of higher doses will be tested.

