5.3. Measures to Minimize Bias: Randomization and Blinding

Randomization

For each cohort, eligible subjects will be randomized at a 3:1 ratio (6 active: 2 control) to receive BGB-DXP604 with or without BGB-DXP593 or placebo. Sentinel dosing will be adopted for each cohort; the randomization ratios for sentinel dosing are provided in Section 3.1.

Site personnel will access the Interactive Response Technology (IRT) system to randomize the treatment assignment. All subjects will receive a unique study subject number. Up to 2 replacements will be allowed for each subject (eg, the original subject in one treatment arm is allowed to have a 2nd replacement when the 1st replacement is withdrawn). A subject for replacement will be assigned to the same treatment as the subject he/she replaces.

Blinding

The study is designed as double-blind for the subjects and the investigator (as well as the site personnel) in order to eliminate observational or performance bias. This is to avoid the systematic differences in assessments on the subject's treatment (ie, BGB-DXP604 with or without BGB-DXP593 or placebo).

The single dose of study drug(s) will be prepared by unblinded pharmacist(s) and administered by blinded study nurse(s). The intravenous infusion of BGB-DXP604, BGB-DXP593, and placebo will be colorless. All follow-up evaluations will be performed by blinded clinic staff.

At the study site, access to the treatment information for each subject is restricted to the unblinded pharmacist(s). Persons directly involved in the clinical conduct of the study will not have access to the treatment allocation before database lock.

Regarding the sponsor, the database of this study will be handled as open label, meaning that the study functions of the sponsor are unblinded (including the medical monitor and study team members from Pharmacovigilance/Drug Safety, Clinical Pharmacology, and Biostatistics with other members as appropriate). The objectives of the study are expected not to be affected.

Unblinding

1. Emergency unblinding

In case of an emergency, the investigator has the sole responsibility for determining if the unblinding of a subject's treatment assignment is warranted. Subject safety must always be the first consideration in making such a determination. Emergency unblinding for AEs may be performed through an IRT system.

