5.5. Dose Interruption or Modification

There will be no dose reduction of study drug(s).

A subject may temporarily interrupt their infusion of study drug(s) or discontinue their infusion of study drug(s) due to infusion-related reactions or other medical events.

The subject should resume the study treatment within 2 hours of the infusion interruption if the AE is resolved or recovered to Grade 1 (whichever is more severe). If the subject is unable to resume the study drug(s) within 2 hours of the infusion interruption, then the subject should be discontinued from the study treatment and the subject will be replaced. The treatment modification for infusion-related reactions is provided in Section 9.8.1.

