9.4.2. Assessment of Severity

The investigator will assess severity for each AE and SAE reported during the study. AEs and SAEs should be assessed and graded based upon the NCI-CTCAE v5.0.

Toxicities that are not specified in the NCI-CTCAE v5.0 will be defined as follows:

- Grade 1: Mild; asymptomatic or mild symptoms; clinical or diagnostic observations only; intervention not indicated
- Grade 2: Moderate; minimal, local or noninvasive intervention indicated; limiting age-appropriate instrumental activities of daily living (ADL)
- Grade 3: Severe or medically significant but not immediately life-threatening; hospitalization or prolongation of hospitalization indicated; disabling; limiting self-care ADL
- Grade 4: Life-threatening consequences; urgent intervention indicated
- Grade 5: Death related to AE

NOTE: The terms “severe” and “serious” are not synonymous. Severity is a measure of intensity (for example, grade of a specific AE, mild [Grade 1], moderate [Grade 2], severe [Grade 3], or life-threatening [Grade 4]), whereas seriousness is classified by the criteria based on the regulatory definitions. Seriousness serves as the guide for defining regulatory reporting obligations from the sponsor to applicable regulatory authorities as described in Section 9.7.2.1.

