9.7.7. Reporting Infusion-Related Reactions

The symptoms of infusion-related reactions may include, but are not limited to, fever, chills/rigor, nausea, pruritus, angioedema, hypotension, headache, bronchospasm, urticaria, rash, vomiting, myalgia, dizziness, or hypertension. Severe reactions may include acute respiratory distress syndrome, myocardial infarction, ventricular fibrillation, or cardiogenic shock. Individual signs and symptoms of an infusion reaction should be recorded each as a separate AE in the eCRF and identified as an infusion-related reaction. Refer to the eCRF completion guidelines for details.

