9.8.1. Managing Infusion-Related Reactions

The symptoms of infusion-related reactions include fever, chills/rigor, nausea, pruritus, angioedema, hypotension, headache, bronchospasm, urticaria, rash, vomiting, myalgia, dizziness, or hypertension. Severe reactions may include acute respiratory distress syndrome, myocardial infarction, ventricular fibrillation, and cardiogenic shock.

Subjects should be closely monitored for infusion-related reactions. Immediate access to an Intensive Care Unit or equivalent environment and appropriate medical therapy (including epinephrine, corticosteroids, intravenous antihistamines, bronchodilators, and oxygen) must be available to treat infusion-related reactions.

Treatment modifications for symptoms of infusion-related reactions due to the study drug(s) are provided in [Table 6](#).

Table 6: Treatment Modifications for Symptoms of Infusion-Related Reactions Due to Study Drug(s)

NCI-CTCAE grade	Treatment modification for Study Drug(s)

Grade 1 - mild Mild transient reaction; infusion interruption not indicated; intervention not indicated.
	
Decrease infusion rate by 50%. Any worsening is closely monitored. Medical management as needed.

Grade 2 - moderate Therapy or infusion interruption indicated but responds promptly to symptomatic treatment (eg, antihistamines, nonsteroidal anti-inflammatory drugs, narcotics, intravenous fluids); prophylactic medications indicated for ≤ 24 hours.
	
Stop infusion. Infusion may be resumed at 50% of previous rate once infusion-related reaction has resolved or decreased to Grade 1 in severity within 2 hours of the infusion interruption. The subject should be discontinued from study drug(s) if the Grade 2 infusion-related reaction has not resolved or decreased over 2 hours of the infusion interruption. Any worsening is closely monitored. Proper medical management should be instituted as described below.

Grade 3 – severe Prolonged (eg, not rapidly responsive to symptomatic medication and/or brief interruption of infusion); recurrence of symptoms following initial improvement; hospitalization indicated for clinical sequelae.
	
Immediately stop the infusion. Proper medical management should be instituted as described below. The subject should be withdrawn from study drug treatment.

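### Read literally, a non-serious infusion-related reaction that is Grade 3 in protocol Table 6 but made up of Grade 1-2 symptoms does not count toward the Grade 3 pausing rule or the Grade 3 overview row

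*SAP*

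**What the plan says.** Four provisions bear on this point.

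- **Recording.** Protocol 9.7.7: "Individual signs and symptoms of an infusion reaction should be recorded each as a separate AE in the eCRF and identified as an infusion-related reaction". No AE record for the reaction as a whole is required. The section refers to the eCRF completion guidelines for details.
- **Grading of AEs.** Protocol 9.4.2: "The investigator will assess severity for each AE and SAE reported during the study". NCI-CTCAE v5.0 is the scale.
- **Grading of reactions.** Protocol 9.8.1, Table 6, sets treatment modifications by the grade of the reaction. Grade 3 covers a prolonged course, "recurrence of symptoms following initial improvement", or sequelae for which hospitalization is indicated. At Grade 3 the infusion is stopped and the subject is withdrawn from study drug.
- **Counting.** SAP 6.5.2 pauses dosing and enrollment in the current cohort on "One or more Grade 3 TEAEs related to study drug(s) as assessed by the investigator in 2 or more subjects at the same cohort". Protocol 3.4 has the same criterion. The AE overview table in SAP 6.5.2 has a row for subjects with Grade 3 TEAEs, and the tables by SOC and PT use the worst grade of the TEAE.

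No text in either document says that the Table 6 grade is recorded, carried to the symptom records, or used in the pausing rule or the tables. SAP 6.5.2 plans no summary of infusion-related reactions.

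**The concern.** The unit that the protocol grades clinically is the reaction, while the unit that the rule counts is the AE record, and for infusion reactions that record is a single symptom. Duration and recurrence describe the course of a reaction. A reaction can be Grade 3 on its course while each symptom, taken alone, is mild or moderate.

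Three things are at stake.

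- **The primary endpoint.** Severity of TEAEs is part of it, and the Grade 3 row is one of its main summaries.
- **Subject protection.** This is the first-in-human study of BGB-DXP604, and protocol 1.5 names this type of event: "the risks of study participation include possible adverse reactions associated with BGB-DXP604, such as infusion-related reactions". If the rule is not met, the protocol continues with replacement. Section 5.5 says of a subject who cannot resume the infusion within 2 hours, "then the subject should be discontinued from the study treatment and the subject will be replaced", and section 5.3 adds "A subject for replacement will be assigned to the same treatment as the subject he/she replaces".
- **Escalation.** Protocol 3.2.2 and 3.3 open the next cohort after SMC review provided that no pausing criterion has been met. The same count therefore bears on the step to 30 mg/kg and on the start of the combination.

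**Working it through.** The plan gives no figure to reproduce. The sample size is expressly non-statistical (3 cohorts × 8 = 24 planned, within the cap of 30), and no reaction rate is stated. The check is a reading of the text, followed by an illustration.

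**Step 1: which Table 6 grades can escape the rule.**

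| Reaction by Table 6 | Other route to a pause | Gap? |
|---|---|---|
| Grade 4 (life-threatening) | Life-threatening events are SAEs (protocol 9.5); one related SAE pauses | No |
| Grade 3, hospitalized | SAE (protocol 9.5); one related SAE pauses | No |
| Grade 3, judged medically significant | SAE (protocol 9.5); one related SAE pauses | No |
| Grade 3 by duration or recurrence, non-serious, at least one related symptom Grade 3 | That symptom record counts | No |
| Grade 3 by duration or recurrence, non-serious, all symptoms Grade 1-2 | None by count | Yes |

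Only the last row is exposed.

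**Step 2: worked case (events assumed).** Two of the 6 active subjects in a cohort have related chills and rash that improve and then recur during the infusion. Both reactions are Table 6 Grade 3 and non-serious, and both subjects are withdrawn. Each symptom is Grade 2. This gives 2 × 2 = 4 AE records.

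| | Symptom grades count | Reaction grade counts |
|---|---|---|
| Subjects with a related TEAE | 2 | 2 |
| Active subjects with a related Grade 3 TEAE | 0/6 | 2/6 (33%) |
| Pausing rule (2 or more subjects) | not met | met |

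If the cohort is not paused, 2 × 1 = 2 replacements are dosed on active treatment. Protocol 5.3 allows up to 2 replacements per subject, so the ceiling is 2 × 2 = 4. That requires both first replacements to be withdrawn too, with no SMC action in between.

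**Step 3: illustration of size.** Let p be the true risk of a non-serious Table 6 Grade 3 reaction in an active subject, and q the share of such reactions that contain a Grade 3 symptom record. Neither is in the documents. With independent subjects and n = 6:

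P(rule met) = 1 − (1 − pq)^6 − 6·pq·(1 − pq)^5

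For p = 0.10 and q = 1: 1 − 0.531 − 0.354 = 0.114 (from unrounded terms).

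| Assumed p | q = 1 | q = 0.5 | q = 0 |
|---|---|---|---|
| 0.10 | 0.114 | 0.033 | 0 |
| 0.20 | 0.345 | 0.114 | 0 |
| 0.30 | 0.580 | 0.224 | 0 |
| 0.50 | 0.891 | 0.466 | 0 |

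The q = 1 column is also what the rule would do if the Table 6 grade counted. The q = 0 column is zero by construction. If exactly 2 subjects have such a reaction, the rule is met with probability q²: 0.56, 0.25 and 0.06 for q = 0.75, 0.50 and 0.25.

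**The case against.** The strongest reply is that there may be no gap in practice. The grade column of Table 6 is headed as an NCI-CTCAE grade, all AEs are graded on that scale, and each symptom is flagged as part of an infusion-related reaction. An investigator could reasonably enter the Table 6 grade on each flagged symptom. The eCRF completion guidelines, which protocol 15.1.2 says data collection should follow, may settle this. The term-specific CTCAE criteria are not in the documents either, so it cannot be shown that a prolonged or recurrent symptom would be graded 1 or 2. All of this stands, and it makes the defect an unsettled reading rather than a certain miscount. It does not remove the defect. The other reading is the literal one, the two readings give opposite pausing results on the same events, and even if the eCRF collects a reaction grade, neither document uses it in the rule or the overview row.

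The second reply is that other safeguards would act. Under protocol 3.4, the SMC's response once it suspects increased risk is worded as a requirement to recommend suspension, although the trigger is a judgement. Sponsor functions, including the medical monitor, are unblinded (protocol 5.3) and sit on the SMC (11.1). The rest of a cohort is dosed only if the first 2 subjects tolerated treatment, and the SMC reviews data before each new cohort. For a reaction during the infusion, the overview rows for discontinuation and treatment modification and the exposure tables would show what happened, and all AEs are listed. This also stands and limits the consequence. None of these safeguards supplies the 2-subject count or the Grade 3 classification.

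A reader might go further and infer that the pausing rule cannot see infusion reactions, or that two withdrawn reactors would go unnoticed. The documents do not support that: serious and life-threatening reactions pause the cohort at one subject, and withdrawals are reported and visible to unblinded SMC members.

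**Conclusion.** The gap is real but narrow, and worth closing. It concerns reactions that are non-serious, Grade 3 only by duration or recurrence, and made up wholly of Grade 1-2 symptoms. For these, the literal text gives 0 where the protocol's own Table 6 gives Grade 3. Two such subjects in a cohort count as 0 against a threshold of 2, and both are absent from the Grade 3 overview row.

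The textual conclusion rests on protocol 9.7.7, 9.4.2 and Table 6 read together with protocol 3.4 and SAP 6.5.2, and on no unseen instruction bringing the Table 6 grade into the count. It does not depend on p or q. The binomial figures show only how far the rule could weaken under assumed rates. They should not be read as expected frequencies: the documents give no reaction rate and describe the risks as generally low.

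**What to change.** State in protocol 3.4 and SAP 6.5.2 that a related infusion-related reaction meeting Table 6 Grade 3 counts as a Grade 3 TEAE for the pausing rule and for the Grade 3 overview row. To support this:

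- capture the Table 6 grade once per reaction in the eCRF;
- count each subject once, at the higher of the reaction grade and the symptom grades;
- report the number and percentage of subjects with a reaction by worst reaction grade and treatment group;
- keep the symptom records, with their own grades, in the SOC and PT tables, so that a Grade 2 rash is not shown as Grade 3.

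The cost is one eCRF field, one summary row, a short protocol amendment and a slightly more sensitive pausing rule. The pausing wording must be amended before it can govern a cohort. The reporting part can be settled before database lock if reaction grades can be recovered from source records.
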